Protocol title: A pilot study of oxidative pathways in MS fatigue

Document Date: 10/12/2016

Version: 4

NCT: 02804594

PI: [name]., PhD
Professor of Clinical Neurology and Pediatrics
UCSF MS Center
Neuroscience Building
[name]
[name]

Protocol title: A pilot study of oxidative pathways in MS fatigue

PI: [name]., PhD
Professor of Clinical Neurology and Pediatrics
UCSF MS Center
Neuroscience Building
[name]
[name]

8. Statistical consideration and analysis plan

8.1 Statistical plan for specific aim 1- To test the tolerability and safety of NAC therapy (1250 mg three times a day) compared to placebo for 4 weeks to treat progressive MS fatigue.

Study Subjects: Target population- Adult patients with progressive MS and fatigue seen at UCSF.

The safety outcome will be analyzed by including all subjects who have received at least one dose of study medication. Participants will be analyzed according to the actual treatment received. The assessment of safety will be based on the frequency of adverse events.

The primary efficacy analysis will be done as an intent-to-treat analysis. Consequently, all randomized participants will participate in the analysis as allocated to NAC or placebo.

8.2 Statistical plan for specific aim 2- To obtain preliminary data on changes in fatigue levels and oxidative pathway biomarkers on NAC therapy in subjects with progressive MS fatigue.

In an intent-to-treat analysis, using Student t-test, the mean change in MFIS score from the baseline to week 4 will be compared between the NAC and placebo groups. The per-protocol secondary analysis will take into account treatment regimen. We will use similar models to compare the changes in brain GSH concentration and blood GSH/GSSG ratio, FSS, NeuroQOL fatigue item bank, 9-hole peg test, 25-foot timed ambulation, and Symbol Digit Modalities Test (SDMT) at the baseline and week fourth between the NAC and placebo groups.

Because there is a possibility for imbalance in the baseline values of potential confounding factors (such as EDSS and depression), an a priori secondary analysis is planned. To assess the effectiveness of NAC vs. placebo, we will use a linear regression model, comparing the mean change in MFIS score from the baseline to week 4, adjusting the models for the baseline EDSS and HADS scores.

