We will use the same models to analyze the change in the severity of fatigue as measured by MFIS and FSS between week 4 (the end of study drug administration period) and week 6 (2 weeks after patients have been off study drug).

Because of the exploratory nature of these analyses, we will not correct our models for multiple comparison testing. Statistical analyses will be performed by a biostatistician from UCSF biostatistics department blinded to treatment assignment.

Sample size calculation: There are no available data to base power calculation for this aim as such a study has never been performed prior. We will use the data generated for this aim to design future studies.

Primary efficacy endpoint: The primary efficacy analysis will be done as an intent-to-treat analysis. Consequently, all randomized participants will participate in the analysis as allocated to NAC or placebo. Using Student t-test, the mean change in MFIS score from the baseline to week 4 will be compared between the NAC and placebo groups. The per-protocol secondary analysis will take in account treatment regimen.

MFIS consists of 21 items with a total score range of 0 to 84 (higher scores indicate worse fatigue). As the primary efficacy endpoint of the trial, we will compare the mean change in total MFIS score from baseline to week 4 visit between intervention and placebo groups.

Secondary efficacy endpoints (differences between treatment groups):

- Per protocol analysis for changes in MFIS from screening /baseline to week 4.
- MFIS subscales changes between screen/baseline and week 4.
- Change in FSS score from baseline to week 4.
- Change in NeuroQOL fatigue item bank score from baseline to week 4.
- Change in 9-HPT score from baseline to week 4.
- Change in 25-FTW from baseline to week 4.
- Change in SDMT score from baseline to week 4.
- Changes in MFIS and FSS between week 4 and 6.

8.3 Statistical plan for specific aim 3- To determine if fatigue severity is associated with baseline spectroscopy and oxidative pathway markers in patients with progressive MS.

We will examine the correlation between biomarkers (spectroscopy and blood oxidation metabolites) and fatigue (MFIS) at baseline. We will use a linear regression model with MFIS score (or its change) as the outcome and the spectroscopy and metabolites as the predictors (in

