separate models). Using data obtained from the control subjects (patients with progressive MS and fatigue severity as measured by MFIS<38) we will also perform a case-control analysis (e.g. logistic regression with being fatigued or non-fatigued as the outcome and spectroscopy or blood metabolites as predictors).

Study variables

Demographic variables: Age, sex, self-reported race/ethnicity (based on the National Institute of Health classification), education (in years) and occupation will be recorded at the screening visit. Because the severity of fatigue may fluctuate during the day and based on the ambient temperature, the time of the visit and the outside temperature will also be recorded.

Baseline MS-related information: Years since disease onset, type of MS (primary versus secondary progressive (per medical records), Expanded Disability Status Scale (EDSS) (obtained at screening visit by the examining physician), and 25-foot timed walk (25-FTW), 9-hole peg test (9-HPT) and Single Digit Modalities test (SDMT) (obtained by a trained technician at screening, baseline and week 4).

Fatigue: MFIS and FSS (questionnaires filled by patients after receiving appropriate instructions from study staff, see appendix) at screening, baseline, week 4 (last study drug dose), and week 6 (2 weeks after stopping study drug).

Depression: Hospital Anxiety and Depression Scale (HADS) depression subscale (questionnaires filled by patients after receiving appropriate instructions from a study staff, see appendix) at screening and baseline.

Quality of life: NINDS NeuroQOL fatigue item bank (questionnaires filled by patients after receiving appropriate instructions from study staff, see appendix) at the screening, baseline and week 4.

Safety laboratory assessment: At screening, CBC and differential, creatinine, AST, ALT, urine analysis and urine pregnancy test will be obtained. At week 4, only creatinine, urine pregnancy test, AST and ALT will be measured.

Research laboratory assessment: Plasma level of reduced glutathione (GSH) and oxidized glutathione (GSSG) baseline and at 4 week visit for patients who enter treatment phase, and baseline research samples will be analyzed for patients who are controls in the study

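### Does Aim 3's optional regression of MFIS change on biomarkers need a treatment-arm term and a stated change window?

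*Combined protocol and SAP*

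**What the plan says.** The title of section 8.3 gives the aim: "To determine if fatigue severity is associated with baseline spectroscopy and oxidative pathway markers in patients with progressive MS". The first sentence of the plan under it is also cross-sectional: "We will examine the correlation between biomarkers (spectroscopy and blood oxidation metabolites) and fatigue (MFIS) at baseline". The regression sentence follows: "We will use a linear regression model with MFIS score (or its change) as the outcome and the spectroscopy and metabolites as the predictors", with each biomarker in its own model. The words in parentheses are the only mention of a change outcome in Aim 3. No arm term, other covariate or change window is given for it.

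Section 8.2 is more explicit about its own regression of MFIS change. That model compares NAC with placebo, "comparing the mean change in MFIS score from the baseline to week 4, adjusting the models for the baseline EDSS and HADS scores". Section 8.2 also lists a second interval among the secondary efficacy endpoints: "Changes in MFIS and FSS between week 4 and 6".

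Under Study variables, plasma glutathione is measured at "baseline and at 4 week visit for patients who enter treatment phase, and baseline research samples will be analyzed for patients who are controls". Week 4 biomarker values therefore exist for treated patients, but only baseline research samples are named for controls.

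The analyst is masked: "Statistical analyses will be performed by a biostatistician from UCSF biostatistics department blinded to treatment assignment". The power paragraph that closes section 8 calls the aim exploratory and gives no sample size.

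**The concern.** A change in MFIS from baseline to week 4 builds up while patients take NAC or placebo, and a treatment effect on that change is exactly what section 8.2 tests. A regression of the same change on a biomarker, with arm left out, invites two worries.

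The first is confounding. If the biomarker were itself moved by NAC, the two arms would differ in both variables, and the pooled slope would show an association that does not exist within either arm. The second is lost precision, because any treatment effect left out of the model goes into the residual variance.

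The unstated window adds a degree of freedom for the analyst. On-treatment change and change after stopping drug are different outcomes, and section 8.2 makes no multiplicity correction. Since these data are meant to inform the design of later studies, a misleading or needlessly imprecise slope would be carried forward.

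**Working it through.** The plan gives no figure for this model, so there is nothing to reproduce. The check has three parts: the reading of the text, the effect of omitting arm on that reading, and the one reading that would cause harm.

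**1. Which predictor and which window?** The aim title and the correlation sentence both put the biomarkers at baseline. The regression sentence does not repeat the time point but sits directly beneath them. Week 4 biomarkers have their own use in section 8.2, where changes in brain GSH and the blood GSH/GSSG ratio are compared between arms, so their collection does not imply a role in Aim 3. For the outcome, baseline to week 4 is the primary efficacy change in MFIS. The week 4 to week 6 interval is a secondary endpoint about the period off drug.

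**2. Baseline biomarker, arm omitted.** Inputs, all assumed because the documents give none: 1:1 allocation; *n* = 10, 15, 20 or 30 per arm; MFIS change *y* = 0.5*m* − *d*·arm + *e*, with *m* and *e* standard normal; *d* = 0, 0.5, 0.8 or 1.0 SD; two-sided 5% test.

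*Bias.* Randomisation makes *m* independent of arm, so the expected slope is the same in both models. In simulation (40,000 trials per setting) the mean slope was 0.50 with and without arm. In a separate run with a true slope of zero and 16, 30 or 60 patients in total, the false-positive rate without arm was 4.2% to 5.4%.

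*Precision.* Two effects oppose each other.

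- Omitting arm raises the residual variance from 1 to 1 + *d*²/4, which multiplies the confidence-interval width by √(1 + *d*²/4). This is √1.0625 = 1.031 at 0.5 SD, √1.16 = 1.077 at 0.8 SD and √1.25 = 1.118 at 1.0 SD.
- Including arm uses one degree of freedom and discards between-arm variation in the biomarker. With *N* patients in total, the width without arm relative to with arm at *d* = 0 is about √((*N*−2)/(*N*−1)) × *t*(*N*−2)/*t*(*N*−3). At *N* = 20 this is √(18/19) × 2.101/2.110 = 0.973 × 0.996 = 0.969, so leaving arm out is about 3% better.

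The two balance when √(1 + *d*²/4) = 1/0.969 = 1.032. Then *d*² = 4 × 0.0645 = 0.258 and *d* is about 0.51. At 30 per arm the same formula gives a ratio of 0.991 and a break-even near 0.27 SD.

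*Power for the slope, with arm vs without arm (simulated):*

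| Per arm | *d* = 0 | 0.5 | 0.8 | 1.0 |
|---|---|---|---|---|
| 10 | 50% vs 53% | 50% vs 50% | 51% vs 47% | 50% vs 45% |
| 15 | 70% vs 72% | 70% vs 69% | 70% vs 66% | 71% vs 63% |
| 20 | 83.5% vs 84.4% | 83.5% vs 82.3% | 83% vs 79% | 83% vs 76% |
| 30 | 95.1% vs 95.5% | 95% vs 95% | 95% vs 93% | 95% vs 91% |

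Across these sizes, the interval without arm is 1–3% narrower at no effect, 0–2% wider at 0.5 SD, 5–7% wider at 0.8 SD and 9–11% wider at 1.0 SD.

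**3. Biomarker change as predictor.** Suppose NAC shifts both the biomarker and MFIS by *d* SD in opposite directions, with no association within arms. The pooled slope is then −(*d*²/4)/(1 + *d*²/4):

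- *d* = 0.5: −0.0625/1.0625 = −0.059
- *d* = 0.8: −0.16/1.16 = −0.138
- *d* = 1.0: −0.25/1.25 = −0.200

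At 15 per arm, the false-positive rate without arm is about 6%, 11% and 19%, against 5% with arm. This is a real hazard, but it belongs to a model that section 8.3 does not describe.

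**The case for a change.** The strongest case for a change is that both omissions are real and that no other part of the supplied text fills them. The regression sentence does not state the biomarker time point, week 4 biomarkers are available, and one added clause would close the confounded reading at no cost in data. Masking is no obstacle, because arm can be entered as a coded variable. If NAC has a large effect, including arm would yield a visibly tighter slope for planning later studies. Deleting the parenthesis would also bring the model into line with the aim's baseline wording.

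Most of this is true as far as it goes. The wording could be fuller, and an analyst who turned to biomarker change should include arm. What does not stand is that the plan as written misleads. The confounded version needs a predictor that goes against the aim title and the sentence before the model. The precision gain needs an effect of 0.8 to 1.0 SD, which nothing in the documents makes likely, and it becomes a small loss if NAC has little effect. Deleting the option would give up an exploratory analysis for which no harm has been shown. The window point is weaker still: one interval is the primary MFIS change, and the other covers the period after drug has stopped.

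**Conclusion.** No change follows. Section 8.3 leaves a covariate and a window unwritten for an optional model in an aim it calls exploratory and for which it makes no power calculation. On the natural reading, MFIS change from baseline to week 4 in randomised patients is regressed on a baseline biomarker. That slope is unbiased and its error rate is sound with or without arm.

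The choice affects precision only: a cost of 0.3 to 2.4 points of power for including arm if NAC is inert, a negligible difference around 0.5 SD, and a gain of 3 to 8 points at 0.8 to 1.0 SD. These sizes rest on assumed inputs (1:1 allocation, 10 to 30 per arm, slope 0.5, unit within-arm residual SD); the absence of bias rests only on randomisation and a baseline predictor. An analyst may sensibly include a masked arm code when fitting the change model, and should report the window used. The baseline regression, the case-control analysis and every efficacy and safety comparison are untouched.
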